Aim 3: Test Phase (18 months) In the second to third year of the proposed project we will test the decision-support tools in a small pilot trial with six providers and thirty patients randomized to the use of the decision support tools. **H1:** Clinicians with access to decision tools will report better acceptability, usability, and less burden when using PST-PC than clinicians without the tools (Acceptability of Intervention Measure, Intervention Appropriateness Measure, Feasibility Of Intervention Measure, System Usability, Modified Self-Efficacy Scale, and User Burden Scales). **H2:** Clinicians randomized to decision support tools will more competently deliver EBPI elements (fewer number of sessions rated below standard by experts and more time to first session rated below standard after certification) than clinicians randomized to unsupported EBPI. **H3:** Patients treated by clinicians with access to decision tools will have better patient-reported outcomes than patients treated by clinicians without access to these tools as assessed with functional disability (Sheehan Disability Scale) and change in depression symptoms over time (PHQ-9). We will conduct preliminary analysis to determine if change in clinical outcomes is mediated by clinician adherence to protocol.

Exploratory Aim: Use the data collected during Aims 1-3 to demonstrate proof-of-concept work on using machine learning and natural language processing to automate and potentially personalize decision support tools.

This study addresses IOM Recommendation 6-3: Conduct research to design and evaluate strategies that can influence the quality of psychosocial interventions, and NIMH SP 4.3 Develop innovative service delivery models to improve dramatically the outcomes of mental health services received in diverse communities and populations

SIGNIFICANCE

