Once a set of sufficiently advanced prototypes have been developed, we will move to the *Build* phase of the project. If the solution is a CDSS, at this point the CMTS developer team will be brought into the design process and the tools and desired functionalities will be described until it is clear to all parties. Feedback on the capacity of the CMTS system to accommodate specific designs will be reviewed. When an adequate agreement on the nature of the designs is achieved, the CMTS development team will build the proposed tools in a development environment. Whatever the solution is, a final prototype will undergo initial feasibility evaluation in pilot field deployments with [name]. He will test the system with one or two clinicians in the BHIP program using the prototype with test patient scenarios. Once we have completed the design of PST-PC support system so that it (1) meets needs of its clinicians (i.e., is useful), and (2) is easy to use and understand (i.e., is usable), we will move to the *Test* phase of this study. Data from this process will be used to inform the Matrix of EBPI Modifications.

Phase 3 / Aim 3: Test Phase (18 months). We will conduct a pilot study comparing clinicians randomized to decision support to clinicians randomized to no support. Six care managers who will each see 30 patients will be identified and complete informed consent. Clinicians at all 13 BHIP sites will be offered the opportunity to participate in the trial.

Patient eligibility. Patient participants will be identified through clinic electronic health records. Participants must be 18 years old or older and suffering from depression (score between 10 and 20 on the PHQ-9). Methods Core research assistants will contact potentially eligible patients to conduct a preliminary screening for eligibility, provide a brief description of the study, and obtain informed consent.

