Clinician recruitment and training. Clinicians will be incentivized to participate in the trial by receiving free training in the PST-PC EBPI, culminating in a certification that can be used for career advancement for these clinical social workers. The training in this EBPI is under consideration to be delivered by the AIMS Center to all clinicians at the BHIP sites within the next several years. The results of the trial will be used to guide the remaining trainings. Six care managers in the BHIP program will be randomized to usual training or training with the use of the smart tools within the CMTS system. We will follow the PST-PC training protocol developed by the AIMS Center, which includes training in basic brief treatment skills, therapeutic elements of the intervention and therapy process. This is followed by simulated case training. Clinicians must pass an introductory session, middle and last session before deploying the intervention with patients. In PST-PC this is determined by obtaining a score of 3 ("satisfactory") or greater on the PST Adherence Scales, which utilizes a Likert-type rating scale (0 = *very poor*, 5 = *very good*). [name] will provide clinician training in PST-PC to all clinicians. Clinicians randomized to the decision support condition will also receive a training manual and in-person training in the use of these tools prior to the initiation of PST-PC training. Once a care manager in either arm of the study is certified to provide PST-PC, they will proceed to the four-month fidelity phase of the trial. Five active patients identified from the existing site registry of each care manager will receive treatment during the trial (30 total).

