Clinician Data Collection. Three types of data will be collected from clinicians: clinician assessment of appropriateness and acceptability, intervention usability, and clinician ability to learn the intervention and maintain competency. To measure **decision support usability**, clinicians will complete the Acceptability of Intervention Measure, Intervention Appropriateness Measure, Feasibility Of Intervention Measure, System Usability, Modified Self-Efficacy Scale, and User Burden Scales, which are core measures for this Center. These scales will be collected through the UWAC data portal after clinicians have completed their intervention with 5 patients. To measure **sustained competency**, clinicians will collect audio recordings of patient sessions for review by experts. [name] will conduct these reviews using the PST Therapist Adherence Scales. Sustained competency will be defined by (1) time to first session rated below average after certification in PST-PC and (2) number of sessions rated as <3 ("satisfactory"). Clinicians will not be given feedback on session performance.

Patient data collection. We will use the UWAC data portal⁴⁹ designed specifically for research on mobile depression interventions to confirm eligibility, complete the consent process, and conduct baseline and outcomes assessment. Patient data will be collect before treatment initiation and after treatment ends. Patients will complete a demographic survey to determine gender, age, ethnicity, income categories, and educational level. Patients will complete a series of brief clinical measures to determine the presence of a depressive disorder and if there are any important comorbidities. The *Sheehan Disability Scale*(SDS)^{50,51} is a brief analog too assess functioning in work, social, and health domains, using visual-spatial, numeric and verbal anchors. The scale has been validated in medical and psychiatric populations with a variety of psychiatric diagnoses.^{50,51} The *9-item Patient Health Questionnaire*⁵² (PHQ-9) consists of 9 DSM depression symptoms and one disability item. It has been found to have excellent sensitivity to change over time (sensitivity = .88, sensitivity = .80).⁵³

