Data Analysis. Aim 3 focuses on pilot feasibility data to inform a larger (future) clinical trial comparing decision support of PST-PC to no decision support. Thus, analyses do not focus on hypothesis-driven inferential statistics but on descriptive statistics, graphical summaries, and basic effect sizes. **H1: Usability.** Differences in clinician reported usability between the two clinician groups will be plotted using a dotplot and tested using a *t*-test using the SUS and UBS as dependent variables. **H2: Fidelity/Competence.** We will compare groups on the proportion of clinicians who reach certification (i.e. score of 3 or greater on treatment competence on at least two sessions). Between treatment differences will be tested with a 2-sample proportion test. (Future analyses with larger sample size will use a generalized linear mixed model approach to account for the nested data.)^{54,55} **H3:**

Patient Reported Outcomes. Histograms and kernel density estimates will be plotted by treatment condition to explore differences on depression outcomes (PHQ-9 total score) and overall daily functioning (SDS). Descriptive statistics (*M* and *SD*) of these outcomes will also be examined by clinician group, using Cohen's *d* as an effect size summary. A *t*-test will be used to examine treatment differences in these patient outcomes. Of ultimate interest is whether the modified treatment (i.e., decision-supported PST-PC vs. unsupported PST-PC) effects patient outcomes through enhanced usability and clinician fidelity. We will use graphical summaries of the data to explore the relationships that are consistent with mediation (e.g., correlation of usability with patient outcomes [b pathway], and treatment differences on patient outcomes with fidelity

partialed out [c' pathway']). The primary focus here is whether the data and relationships appear consistent with mediation, as opposed to a formal test, which will be dramatically under-powered.

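### Clinician usability and burden scales are collected only after five completed patients, with no fallback for a clinician who does not get there, so H1 can be biased in either direction if stopping is related to burden

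*Combined protocol and SAP*

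**What the plan says.** The Clinician Data Collection section lists six instruments, among them System Usability and User Burden, and gives one collection time for all of them: "These scales will be collected through the UWAC data portal after clinicians have completed their intervention with 5 patients".

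Whether five patients is the whole caseload depends on two statements that disagree. The Clinician recruitment and training section says: "Five active patients identified from the existing site registry of each care manager will receive treatment during the trial (30 total"). The Phase 3 / Aim 3: Test Phase paragraph says: "Six care managers who will each see 30 patients will be identified and complete informed consent".

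Two further steps come before that time point. On certification, "Clinicians must pass an introductory session, middle and last session before deploying the intervention with patients". Once certified, "they will proceed to the four-month fidelity phase of the trial".

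The hypothesis in the Specific Aims (Aim 3, H1) is directional: "Clinicians with access to decision tools will report better acceptability, usability, and less burden when using PST-PC than clinicians without the tools". Under Data Analysis, the differences between clinician groups "will be plotted using a dotplot and tested using a *t*-test using the SUS and UBS as dependent variables".

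For the Test phase the document gives no baseline, interim, fixed-date or early-stop collection of these scales, no analysis set for clinicians, and no missing-data rule for H1. The SUS ratings under Phase 2 / Aim 2 are of prototypes during design and do not fill this gap.

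**The concern.** Whether an H1 score exists depends on a clinician finishing the caseload. Burden and poor usability, which H1 measures, are plausible reasons for not finishing. Followed as written, the rule makes H1 a comparison of completers, and availability of the outcome may depend on its value.

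Non-completion is not far-fetched on the plan's own terms. The H2 analysis compares the proportion of clinicians who reach certification, so the plan allows that some may not. The Power and Sample Size section lists retention and attrition among the things the pilot is to measure. The Significance section attributes low uptake of decision support partly to perceived burden.

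With six clinicians in all, one missing score is a large share of the data and no model can recover it. The stake is less a test result than the dotplot and effect size carried into the future trial. The exploratory correlation of usability with patient outcomes would also lose that clinician.

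**Working it through.** **Inputs from the document.** Six clinicians are randomised ("Six care managers in the BHIP program will be randomized to usual training or training with the use of the smart tools within the CMTS"). Patients per clinician are five or 30, depending on the paragraph. The total is 30 patients, also stated in Specific Aims (Aim 3) and Study Overview. No clinician dropout rate, SD, alpha or allocation ratio is given.

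**Assumptions.** Three clinicians per arm, independent normal scores with a common SD, no true difference, and scores oriented so that higher is more favourable (UBS reversed if needed).

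**1. Is five the full caseload?** 6 × 5 = 30, which reproduces the stated total. 6 × 30 = 180, which does not. On the second wording the scales would fall early in a clinician's caseload, and the concern would weaken sharply.

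**2. Shift if the least favourable of three scores is missing.** The expected minimum of three standard normal draws is −0.846. The three have mean zero, so the other two have mean 0.846 / 2 = 0.42 SD. A simulation of 1,000,000 draws agrees. The shift in the difference (tool minus control) is:
- lowest scorer lost in the tool arm only: +0.42 SD
- lowest scorer lost in the control arm only: −0.42 SD
- lowest scorer lost in both arms: 0
- two lowest lost in the tool arm only: +0.85 SD
- no loss: 0

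For an assumed SUS SD of 10, 15 or 20 points, 0.42 SD is about 4, 6 or 8 points.

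**3. Allowing for the loss being uncertain.** Expected shift = p × 0.423 SD, where p is the assumed chance that the lowest scorer in one arm is lost:
- p = 10%: 0.04 SD
- p = 25%: 0.11 SD
- p = 50%: 0.21 SD

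**4. A second model.** Suppose every tool-arm clinician scoring below k SD stops, and no control does. The chance of losing at least one of three is 1 − (1 − Φ(k))³, and the bias in the expected score of those who remain is φ(k) / (1 − Φ(k)):
- k = −1.5: 19% and 0.14 SD
- k = −1: 40% and 0.29 SD
- k = −0.5: 67% and 0.51 SD

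**5. Precision, for scale.** The 95% half-width for the arm difference is t(0.975, 4) × √(1/3 + 1/3) = 2.776 × 0.816 = 2.27 SD with 3 v 3. With 2 v 3 it is t(0.975, 3) × √(1/2 + 1/3) = 3.182 × 0.913 = 2.91 SD. The second figure takes the SD as unchanged, which suits a loss unrelated to the score. It should not be paired with the 0.42 SD shift, which supposes that the lowest scorer is the one lost.

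**The case against.** A reader might infer that H1 is biased toward the tool. The documents do not support that, for four reasons.

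- They give no clinician dropout rate and no indication that any clinician will stop. They are silent on surveying those who do, and do not rule it out. With no loss the bias is zero.
- The trigger and the certification requirement apply to both arms. A control clinician may stop because unsupported PST-PC is burdensome, and that loss moves H1 against the tool.
- Giving up the tool is not giving up the patients. The Specific Aims note that clinicians often ignore decision support. A clinician who does so but still treats five patients gives a score, presumably a poor one.
- Prototypes are iterated to a SUS of at least 80 and the final one is field-tested before the Test phase. This lowers the chance of quitting because of the tool, but does not remove it.

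Two further arguments have weight. Rating after five patients gives every clinician equal exposure, which is a sound reason for the trigger. And Data Analysis describes Aim 3 as mainly descriptive; with a half-width of 2.27 SD on complete data, H1 is imprecise with or without this gap.

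These points settle the direction and the severity, and they argue against replacing the trigger. They do not close the gap: a clinician who falls short of five still has no planned score. A descriptive pilot with six points is also where a missing one matters most to the picture.

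**Conclusion.** The concern holds as a conditional risk. As written, the plan collects no H1 score from a clinician who stops early, is not certified, or does not reach five patients. If such losses are related to burden, H1 can be biased, with a sign that depends on the arm in which they fall. The size is about 0.42 SD for certain loss of the lowest scorer in one arm, and 0.04 to 0.21 SD in expectation for an assumed 10% to 50% chance of that loss. This rests on an assumed 3:3 split, normal scores, assumed loss probabilities, and five patients being the full caseload. Given the pilot's descriptive purpose, the change is a cheap improvement and not a condition for the trial's validity.

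**What to change.** Keep the five-patient trigger and add to the Clinician Data Collection section: *or, for any randomised clinician who has not completed five patients, at the time the clinician stops taking part or at the end of the four-month fidelity phase, whichever is first.* An uncertified clinician never enters the fidelity phase, so for that clinician the stopping time applies.

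Show the number of patients completed beside each clinician's point in the dotplot, and report clinician discontinuation and its reason by arm.

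Reconcile the Test Phase paragraph (30 patients per care manager) with the Clinician recruitment and training section (five each, 30 in total), because the meaning of the trigger depends on it.

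The cost is one sentence, a portal reminder and a label on the plot. The downside is that some ratings will rest on fewer than five patients, possibly none, so exposure will not be equal for those clinicians. The label makes that visible.

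### The H2 count of low-rated sessions has no denominator, so it mixes quality per session with the number of sessions rated

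*Combined protocol and SAP*

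**What the plan says.** All references are to the Combined protocol and SAP.

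- **Specific Aims, Aim 3 (H2)** treats as more competent the arm with "fewer number of sessions rated below standard by experts and more time to first session rated below standard after certification".
- **Clinician Data Collection** defines sustained competency by two measures: (1) "time to first session rated below average after certification in PST-PC and (2) number of sessions rated as <3". The first uses a below-average threshold and the second uses <3. The material comes from the clinicians themselves: "clinicians will collect audio recordings of patient sessions for review by experts".
- **Clinician recruitment and training** says of certified care managers that "they will proceed to the four-month fidelity phase of the trial". It assigns five patients to each care manager, 30 in total.
- **Phase 3 / Aim 3: Test Phase** says instead: "Six care managers who will each see 30 patients will be identified and complete informed consent".
- **Data Analysis** states for H2: "We will compare groups on the proportion of clinicians who reach certification", with a two-sample proportion test. Neither sustained-competency measure appears there. The section describes the Aim 3 analyses as descriptive pilot work.

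No section gives the sessions per patient, the number or selection of recordings to be rated, a denominator for the count, the unit of time, or the handling of a clinician who has no low-rated session.

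**The concern.** The expected number of low-rated sessions is the number of sessions rated times the chance that a session is rated low. Only the second factor is competence. The first depends on attendance, dropout, scheduling and how many recordings a clinician submits, none of which the plan fixes. Because H2 reads fewer low sessions as better, a clinician with fewer rated sessions will tend to look better at equal quality.

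Volume could differ between arms in two ways: the tools might change how much treatment is delivered or recorded, or six clinicians might differ by chance. In either case the arms would differ on measure (2) without differing in competence.

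Measure (1) has a related weakness. If time means calendar time, which is the natural reading but is not stated, the first low-rated session comes sooner when sessions are closer together.

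Sustained competency is the study's target mechanism, and the pilot is meant to inform a larger trial, so an ambiguous measure would be carried forward.

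**Working it through.** **The plan's own figure.** 6 care managers × 5 patients = 30, which matches the total under Clinician recruitment and training. The Test Phase sentence, read literally, gives 6 × 30 = 180. The two passages must be reconciled before anyone can say how many sessions to expect.

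**Inputs from the documents.** Six clinicians, a four-month phase and five patients each.

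**Assumptions, because the documents give no values.** Three clinicians per arm (the allocation ratio is not stated); 4, 6 or 8 sessions per patient, so n = 20, 30 or 40 rated sessions per clinician; a chance p of a low rating of 0.1 to 0.3, the same for every session and clinician; sessions evenly spaced over 17.4 weeks.

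**Step 1: expected count per arm = 3 × n × p.**

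| p | n = 20 | n = 30 | n = 40 |
|---|---|---|---|
| 0.1 | 6 | 9 | 12 |
| 0.2 | 12 | 18 | 24 |
| 0.3 | 18 | 27 | 36 |

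The ratio between arms equals the ratio of sessions: 1.5 for 30 against 20, and 2 for 40 against 20, whatever p is.

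**Step 2: how often the lower-volume arm looks better at equal quality.** This is a binomial simulation with 400,000 runs and 20 sessions per clinician in the lower-volume arm.

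| p | Lower count, against 30 | Lower count, against 40 | Lower proportion, against 30 | Lower proportion, against 40 |
|---|---|---|---|---|
| 0.1 | 75.1% | 91.7% | 48.3% | 47.4% |
| 0.2 | 86.9% | 98.5% | 48.5% | 47.8% |
| 0.3 | 93.6% | 99.8% | 48.7% | 48.0% |

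With equal volume (30 against 30), one given arm has the lower count in 45.0% to 46.8% of runs; ties and the other arm make up the rest. Dividing by rated sessions brings the unequal-volume cases close to that level.

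**Step 3: a worse clinician can have the lower count.** 20 sessions at p = 0.3 gives 6 expected low sessions; 40 sessions at p = 0.2 gives 8.

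**Step 4: time to first low-rated session.** The mean wait in weeks, with no event counted as 17.4, is (17.4/n) × [1 − (1 − p)^n]/p.

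| p | n = 20 | n = 30 | n = 40 |
|---|---|---|---|
| 0.1 | 7.64 | 5.55 | 4.29 |
| 0.2 | 4.30 | 2.90 | 2.17 |
| 0.3 | 2.90 | 1.93 | 1.45 |

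At p = 0.1 the chance of no low-rated session at all is 0.9^n: 12.2%, 4.2% and 1.5% for n = 20, 30 and 40. A censoring rule is therefore needed.

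**The case against.** **The measure is not tested.** Data Analysis compares the arms for H2 only on the proportion certified, in a pilot declared descriptive and sized for practical reasons. This stands. A reader might infer that the trial cannot answer H2 because of the count, or that its conclusion could be reversed. The documents do not support that: no planned between-arm comparison uses either measure, so there is no planned conclusion to reverse. A descriptive summary can still mislead, and nothing in the plan promises the denominator.

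**Unequal volume is conjecture.** This also stands. The aim of reducing obstacles to delivery says nothing about session numbers, and five patients over four months partly standardises exposure. With equal volume and pace there is no systematic bias. The calculations show what follows if volume differs, not that it will.

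**Few sessions do not guarantee a good score.** A reader might infer that a clinician whose patients leave after one visit scores best on both measures. That does not follow. Five single visits still give a 1 − 0.8^5 = 67% chance of at least one low rating at p = 0.2. A clinician with none would ordinarily be censored early, which is little information rather than a long time. The plan states no rule that scores it as best.

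**Elapsed time may be the right scale.** The Impact section is concerned with drift in competency. If skill fades with calendar time, counting in sessions would distort in the opposite direction, because a slow clinician would reach the same decay at a lower session number. This stands, and it is a reason to show both scales.

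**A proportion does not cure selective recording.** Correct. If weak sessions go unrecorded, the proportion is biased too.

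**Conclusion.** The concern holds for the count. Measure (2) has no denominator, and the number of rated sessions is fixed nowhere, so the count cannot separate quality per session from volume. If rated sessions differ by a factor of 1.5, the expected counts differ by the same factor at equal competence: 18 against 12 at an assumed 20% rate, with 9 against 6 and 27 against 18 at 10% and 30%. These figures rest on assumed session numbers, three clinicians per arm and one common low-rating rate. Real variation between clinicians would blur the pattern but would not remove the dependence on volume.

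The consequence is limited to the descriptive reading of H2. It may extend to the mediation plots, where fidelity is partialed out but the fidelity measure is not named. For measure (1), the defect is an unstated time scale and censoring rule and a threshold worded differently from measure (2); elapsed time itself is not a wrong choice. This is a low-cost improvement that should be made, not a flaw that invalidates the pilot.

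**What to change.** 1. **Clinician Data Collection, measure (2):** define it for each clinician as the number of rated sessions scored <3 divided by all rated sessions.
2. **Measure (1):** use the same <3 cut-off, state that time is elapsed time from certification and in what unit, and censor at the clinician's last rated session. Show the session number of the first low-rated session beside the elapsed time, not in its place.
3. **Data Analysis, H2:** add both measures as descriptive summaries, with the numbers of sessions delivered, recorded and rated by arm. With six clinicians, a six-row listing is enough.
4. **Patients per care manager:** reconcile the Test Phase sentence with Clinician recruitment and training.

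The same recordings and ratings serve; the additions are wording, one table and a log of delivered and recorded sessions. There are two downsides. The proportion is imprecise for a clinician with few rated sessions, which the displayed denominator makes plain. Selective recording can still bias it, and the displayed counts reveal gaps between sessions delivered and rated without correcting for them.

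### H2 is about sustained competency after certification, but the only analysis specified for H2 compares the proportion of clinicians who become certified

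*Combined protocol and SAP*

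**What the plan says.** In Specific Aims, Aim 3, H2 predicts that clinicians with the decision tools will have "fewer number of sessions rated below standard by experts and more time to first session rated below standard after certification".

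Clinician Data Collection lists both learning and maintenance among what is to be measured: "clinician ability to learn the intervention and maintain competency". For the maintenance part, "clinicians will collect audio recordings of patient sessions for review by experts", and sustained competency is defined by (1) "time to first session rated below average after certification in PST-PC and (2) number of sessions rated as <3".

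Clinician recruitment and training sets the order of events: "Once a care manager in either arm of the study is certified to provide PST-PC, they will proceed to the four-month fidelity phase". Before that, "Clinicians must pass an introductory session, middle and last session before deploying the intervention with patients".

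The Data Analysis section opens by saying that the pilot will rely mainly on descriptive statistics, graphs and effect sizes. Under H2 it then states: "We will compare groups on the proportion of clinicians who reach certification". Certification is glossed there as a competence score of 3 or more on two or more sessions, and the arms are compared with a two-sample proportion test. A mixed model for nested data is left to future, larger studies. No other H2 analysis is given.

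**The concern.** The analysed variable is not the hypothesised one. Specific Aims and the purpose statement in Significance both make sustained skill the study's target. Yet the only H2 statistic concerns whether a clinician gets as far as the period in which sustained skill can be observed.

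Three things are at stake:

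- How to summarise the two H2 endpoints is left open until the ratings have been seen.
- The low-rating rate and its spread between clinicians, which would inform a larger trial, are not specified outputs.
- The mediation plots use fidelity, but the plan does not say which summary of the session ratings that means. Aim 3 calls the mediator adherence to protocol, and Clinician Data Collection names the rating scale; neither fixes the summary.

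**Working it through.** The plan states no power, alpha or expected rate for H2, so there is no figure to reproduce. The check is mainly a comparison of texts.

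**1. The texts side by side**

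| Section | What it names for H2 | When it can be observed |
|---|---|---|
| Specific Aims, Aim 3 | Number of low-rated sessions; time to the first one | After certification |
| Clinician Data Collection | The same two, from recorded patient sessions | After certification |
| Data Analysis, H2 | Certified, yes or no | At entry to the fidelity phase |

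The words for *after certification* are attached literally only to the time endpoint. The count is post-certification by context, because it is taken from patient sessions and clinicians must pass their sessions before they treat patients.

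**2. Could certification stand in for either endpoint?** If the two or more qualifying sessions are training sessions, certification is settled before any patient session is rated. If they are patient sessions, one yes/no value for two passing scores is still neither a count of sessions below 3 nor a time to the first. The mismatch holds on both readings.

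**3. Does the general promise of descriptive statistics fill the gap?** H1 names its scales and a dotplot. H3 names the PHQ-9 and SDS with histograms, means, SDs and Cohen's *d*. H2 names certification only.

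**4. What the specified comparison can yield**

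Inputs from the documents: six care managers, five patients each, 6 × 5 = 30 patients. (The Phase 3 paragraph can be read as 30 patients per care manager; Specific Aims, Study Overview, Clinician recruitment and training and Clinician Data Collection support 30 in all, five each.) Assumptions: independent clinicians, 3:3 allocation where it matters, and the certification rates shown. The documents give neither the ratio nor the rates.

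If all six certify, the difference is 1 − 1 = 0 and the pooled variance is 1 × (1 − 1) × (1/3 + 1/3) = 0, so z = 0/0. The probability of this is p⁶ for a common rate p:

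| Assumed rate p | P(all six certify) = p⁶ | P(at least one does not) = 1 − p⁶ |
|---|---|---|
| 0.70 | 0.118 | 0.882 |
| 0.80 | 0.262 | 0.738 |
| 0.90 | 0.531 | 0.469 |
| 0.95 | 0.735 | 0.265 |

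With unequal rates and 3:3 allocation it is a³b³: 0.70³ × 0.95³ = 0.294, and 0.80³ × 0.95³ = 0.439.

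The last column matters too. If any clinician fails to certify, a summary of sustained competency covers only a certified subset and no longer the randomized six.

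**5. Precision of a direct summary**

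Let q be the proportion of sessions rated below 3, n the sessions reviewed per clinician and ICC the within-clinician correlation, all assumed. With 3 v 3 clinicians, the standard error of the arm difference in mean clinician-level proportion is

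SE = √[(2/3) × q(1 − q) × (ICC + (1 − ICC)/n)]

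- Smallest case (q = 0.10, n = 30, ICC = 0): √(0.06 × 0.0333) = 0.045
- Middle case (q = 0.20, n = 20): √(0.1067 × 0.05) = 0.073 at ICC 0; √(0.1067 × 0.24) = 0.160 at ICC 0.20
- Largest case (q = 0.30, n = 10, ICC = 0.20): √(0.14 × 0.28) = 0.198

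The formula ignores clustering of sessions within patients. With 3 v 3, a clinician-level permutation test cannot give a two-sided p below 2/C(6,3) = 2/20 = 0.10. A direct summary of the endpoints is therefore descriptive by necessity.

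**The case against.** The strongest defence is that this is a six-clinician pilot. Data Analysis disclaims hypothesis-driven inference, and Power and Sample Size says that the sample was not set by power. No confirmatory conclusion is at risk. That caps the severity, but it does not supply the missing summary: a descriptive pilot still has to describe the quantities in its own hypothesis.

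A second argument is that Data Analysis gives its own gloss of certification, under a fidelity and competence label, so it might be a coarse fidelity measure taken on patient sessions. The wording leaves room for this, although Clinician recruitment and training plainly puts certification before the fidelity phase. Even on that reading, it is neither of the two named endpoints.

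Third, the deferred mixed model might be said to cover session-level data. It belongs to future studies, and the text does not say what is nested in what. It neither fills the gap nor proves it.

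Fourth, the numerical illustrations rest on assumed rates, session numbers and ICCs. That is correct, and the finding does not need them.

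One practical objection stands. The plan does not say how many or which recordings are reviewed, or in what unit time is counted. If only some sessions are reviewed, the first low rating found may not be the first low session. These details have to be settled along with the analysis wording.

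**Conclusion.** The concern holds. Followed as written, the H2 analysis does not answer H2: it compares six yes/no values on certification and specifies no between-arm summary of either sustained-competency endpoint. This follows from the text alone and does not depend on power.

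Under the stated assumptions, the chance that the single specified test is undefined runs from 0.12 to 0.74 for common certification rates of 70 to 95%. A direct comparison of low-rating proportions would be imprecise, with a standard error of about 0.05 to 0.20, but it would at least address the hypothesis.

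This should be fixed, but it does not undermine the study. It is a descriptive pilot, the recordings and expert ratings are already planned, and an amendment before analysis loses nothing, provided the number of sessions reviewed and their timing are recorded.

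**What to change.** In the H2 paragraph of Data Analysis, add a descriptive summary by clinician and by arm of:

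1. the number and proportion of reviewed post-certification sessions rated below 3, with sessions reviewed as the denominator;
2. the time from certification to the first session rated below 3, with clinicians who have none marked as censored at their last reviewed session. State the unit of time.

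Show all six clinicians. Give the arm difference in mean clinician-level proportion below 3 as the effect size; no p-value is needed. State how many sessions are reviewed per clinician and how they are chosen.

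Keep the certification proportion as a separate learning outcome over all randomized clinicians. Note that if any clinician does not certify, the sustained-competency summary covers only the certified subset.

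Make three wording changes in the same edit:

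- Use one threshold wording for both endpoints. Aim 3 refers to a standard for both, while Clinician Data Collection refers to an average for one and to a score below 3 for the other.
- Reconcile the two-session gloss of certification in Data Analysis with the three-session pass requirement in Clinician recruitment and training, which is not expressly called the certification rule.
- State which summary of the adherence ratings is the fidelity variable in the mediation plots.

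The cost is SAP wording, one per-clinician table and plot, and a record of the sessions reviewed for each clinician. No new ratings are needed.
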